### Day 21-28

Standard of care clinical followup, H&P, labwork, MRI or CT imaging.  
PK blood draw at 3-4 weeks.

Please see appendices for additional study calendar.

### 5.3 Duration of Therapy

There will be one cTACE procedure performed at baseline, done as standard of care. PK blood sampling will continue until the 3-4 week time point.

### 5.4 Duration of Follow-up

Patients will return 3-4 weeks after the cTACE for clinic visit, H&P, laboratory tests, and new imaging as part of standard of care. The final PK blood sample will be drawn at this time.

### 5.5 Criteria for Removal from Study

A study participant may be removed from the study for any of the following reasons:

- At the request of the patient or a representative, i.e., withdrawal of consent.
- Patient falls out of eligibility criteria
- Technical failure of the cTACE procedure
- Use of illicit drugs or other substances that may, in the opinion of the investigator, contribute to toxicity
- The patient is lost to follow-up
- Death

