### 1.5 Lobar and Superselective TACE

The lobar conventional TACE approach consists of the administration of chemotherapy and Lipiodol to via the left or right hepatic lobar branch followed by embolization. As a consequence of this approach, a large region of the liver is treated which would make it suitable for cases where there are multiple lesions within a lobe. However, this technique was also correlated to a high serum concentration of the chemotherapeutic drug after administration, which compared unfavorably to an alternate form of treatment, the drug-eluting bead TACE (DEBTACE).

While the lobar technique is still very much in use today, TACE protocols have been refined and new specialized protocols developed. The superselective approach would advance the microcatheter further into the hepatic arterial branch afferent to the segment in which the tumor is located, or if possible the tip of the catheter will be further advanced into the subsegmental branches feeding the tumor, where chemotherapy will be administered followed by embolization. In this manner, the chemotherapy is delivered in a more selective fashion, sparing more of the healthy liver parenchyma.

Logistically, the superselective approach introduces new complexities including a lengthier operation and being more technically demanding, but some studies have observed that the superselective approach may result a higher rate of complete tumor necrosis with small HCCs in comparison to the lobar approach (27-29). In Golfieri's study, tumor necrosis was greater in the superselective arm vs the lobar arm (75.1% vs 52.8%), and complete tumor necrosis was observed in approximately two times more patients on the selective arm when compared to the lobar nonselective arm, which also resulted in a reduced need for further treatments (27). The damage to liver parenchyma and function was also reduced with the superselective approach, with less adverse events when compared to the nonselective TACE (28). A superselective or subsegmental approach could also be performed in patients who may be contraindicated for conventional nonselective TACE due to severe cirrhosis and risk of serious ischemic complications (30, 31). Given the reduced adverse event profile of the subsegmental approach and the selective nature of treatment, it is conjectured that the serum doxorubicin concentration would also be decreased.

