### 4.2 Registration Process

Patients consented for the study will be registered with OnCore, Yale's Clinical Trials Management System, and be assigned a study identifier and counted for the final data analysis. Patients' progress while on the study will be managed via OnCore.

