## 6.3 Adverse Event Capture and Reporting

Risks associated with the research procedures are expected to be minimal, and are involved with the drawing of blood and the placement of the IV catheter (second sheath). They include pain, bruising, swelling and bleeding when the catheter is placed. There is also a risk of infection at the IV site, and very rarely, nerve damage.

HIC #: 1506016008  
[name]

Adverse Events are collected through 3-4 weeks post cTACE and documented for each patient on the AE case report form (CRF). The AEs are transcribed onto a study-specific electronic AE log which is reviewed regularly by the PI and is available for the IRB and monitoring committees for review.

Study deviations (protocol deviations: PDs) are collected and reported in the same way as the AEs are managed. PDs are collected through 3-4 weeks post cTACE, and documented on CRFs and into PD electronic logs, which are reviewed regularly by the PI and available for IRB and monitoring committees for review.

Unanticipated Problems Involving Risks to Subjects and Others (UPIRSOs) that may require a temporary or permanent interruption of study activities will be reported immediately (if possible), followed by a written report within 5 calendar days of the Principal Investigator becoming aware of the event to the IRB (using the appropriate forms from the website) and any appropriate funding and regulatory agencies. The investigator will apprise fellow investigators and study personnel of all UPIRSOs and adverse events that occur during the conduct of this research project via email as they are reviewed by the PI. The Cancer Center Protocol Review Committee (PRC), Yale Cancer Center Data and Safety Monitoring Committee (DSMC), study sponsor, funding and regulatory agencies will be informed of serious adverse events within 5 days of the event becoming known to the Principal Investigator.

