### 7.2 Secondary Outcome Variables

Feasibility:

- Technical success of the cTACE procedure (technical failure is defined as the inability to administer the cTACE material, in which case the patient would be excluded from the study)
- Dose of doxorubicin delivered

Safety:

- All toxicities assessed as being at least possibly related, up to the 3-4 week follow-up visit (post cTACE) will be collected. Toxicities will be analyzed by descriptive statistics to show type, grade (NCI Common Toxicity Criteria v4.0), frequency and time from cTACE.

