## 8.2 Case Report Forms

As used in this protocol, the term case report form (CRF) refers to a paper form. A CRF is required and should be completed for each included subject.

The investigator has ultimate responsibility for the accuracy, authenticity, and timely collection and reporting of all clinical, safety, laboratory data entered on the CRFs and any other data collection forms.

All CRFs must be signed by the investigator to verify that the data contained on the CRFs is accurate. Any corrections to entries made in the CRFs and source documents must be dated, initialed, and explained (if necessary) and should not obscure the original entry.

Usually, source documents are the hospital's or the physician's subject medical chart. In these instances the data collected on the CRFs must match the data in the corresponding charts. A CRF, or part of the CRF, may also serve as a source document.

Electronic master logs of all adverse events and protocol deviations will also be recorded and kept in an encrypted database with access only available to study team members. An individual physical paper CRF will also be kept with the patient's research binder.

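### The rule excluding technical failures is not limited to the PK analysis and no safety set is defined, so adverse events from an attempted but failed procedure can drop out of the safety summary

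*Combined protocol and SAP*

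**What the plan says.** **Text that takes the patient out.** Section 7.2 states: "technical failure is defined as the inability to administer the cTACE material, in which case the patient would be excluded from the study". The synopsis (secondary outcomes, feasibility) and Section 2.2 say the same. Section 5.5 is softer. It opens with "A study participant may be removed from the study for any of the following reasons" and then lists "Technical failure of the cTACE procedure" alongside withdrawal of consent, loss to follow-up and death.

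**Text on collecting safety data.** The safety outcome in Section 7.2 reads: "All toxicities assessed as being at least possibly related, up to the 3-4 week follow-up visit (post cTACE) will be collected". It is summarised by type, grade, frequency and time from cTACE. Section 6.3 says: "Adverse Events are collected through 3-4 weeks post cTACE and documented for each patient on the AE case report form (CRF". Section 8.2 adds: "A CRF is required and should be completed for each included subject".

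**Text that keeps the patient in.** Under Section 4.2, consented patients are registered, to "be assigned a study identifier and counted for the final data analysis". Section 6.3, as quoted, refers to each patient. Reporting of serious adverse events and of unanticipated problems (Sections 6.3 and 8.1) has no exception for a failed procedure.

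**What is absent.** No section defines a safety analysis set, says that events already recorded are kept after removal, or says that follow-up continues after a failed attempt.

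**The concern.** A technical failure is a patient in whom the material could not be given. By then the patient may already have had arterial access and catheterization, which come before injection in the procedure described in Section 5.1.1. If an access or vessel complication stops the injection, one event is both the safety outcome and the reason for exclusion. Removing that patient from the safety summary makes membership of the analysis depend on the outcome being measured.

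Excluding such a patient from the PK parameters is sensible, because there is no doxorubicin exposure to describe. That reason does not carry over to safety. What is at stake is the completeness of a descriptive secondary outcome, and of adverse-event follow-up to 3-4 weeks for patients who underwent an attempt.

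**Working it through.** The plan states no figure on this point, so the check is mainly a reading of the sections against each other.

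**Step 1: scope of the exclusion.** The synopsis and Sections 2.2 and 7.2 exclude the patient from the study as a whole. None of them limits this to PK, and in each the safety outcome follows directly with no carve-out. Section 5.5 makes removal discretionary. Discretion does not solve the problem, since the decision could be taken after the complication is known.

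**Step 2: route by which events are recorded.** Events go on the CRF (6.3), and a CRF is required for each included subject (8.2). A patient excluded from the study falls outside that requirement on its plain wording.

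**Step 3: the time window.** Collection runs to 3-4 weeks after cTACE (6.3, 7.2), and the visit is dated from cTACE (5.4). If no material was given, the documents do not say what starts the window.

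**Step 4: text in the other direction.** Sections 4.2 and 6.3 would keep the patient in. No order of precedence is given, so both readings are open.

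**Step 5: direction of any error.** Let n be attempts, k failures, a the patients with an event among those treated, and b those with an event among failures.

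- All attempts: (a + b)/n
- Failures excluded: a/(n − k)

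Exclusion understates the rate only if b/k exceeds a/(n − k). It makes no difference if the two are equal, and overstates the rate slightly if failures have fewer events.

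To show what one patient does, take n = 30, k = 1 and, as an assumption, a = 3 (roughly the 10% complication rate in Section 1.6 applied to 29 patients):

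| Case | All attempts | Failure excluded |
|---|---|---|
| Failed patient had no event (b = 0) | 3/30 = 10.0% | 3/29 = 10.3% |
| Failed patient had an event (b = 1) | 4/30 = 13.3% | 3/29 = 10.3% |

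This shows the mechanism and is not a forecast.

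**Step 6: how many patients.** The documents give no failure rate, so f is an assumption. With 30 attempts (the planned enrolment), expected failures are 30f and the chance of at least one is 1 − (1 − f)^30.

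| Assumed f | Expected failures | Chance of at least one |
|---|---|---|
| 1% | 0.3 | 26% |
| 2% | 0.6 | 46% |
| 5% | 1.5 | 79% |
| 10% | 3.0 | 96% |

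Over this range, at most a few patients are affected.

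**The case against.** The strongest reply is that no section orders adverse events to be deleted or collection to stop. Section 5.5 reads as a list of ways participation ends. It includes death, and nobody would infer that deaths leave the safety summary. The firmer exclusion wording sits inside the technical-success item of a PK study and could be meant for the PK cohort. Sections 4.2 and 6.3 would keep the patient, and serious events are reported individually whatever the procedure's outcome. The affected group is narrow, because a complication during partial administration is not clearly a failure. Safety is descriptive, and Section 7.4 has no stopping rule that uses it.

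Most of this stands as a limit on the claim. It does not remove the problem. The exclusion is stated three times without qualification, and individual reporting of serious events does not place non-serious events in the summary.

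A reader might also infer more than the documents support:

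- **That toxicity is biased downward as a matter of fact.** Loss of events follows from one side of conflicting sections. Even then, understatement requires failed attempts to carry more events than completed ones.
- **That the bias differs by arm.** Section 1.5 describes the superselective approach as "a lengthier operation and being more technically demanding", but gives no failure rate. It also reports fewer adverse events with that approach, and Section 5.1.1 accepts segmental placement where subsegmental placement is not possible. A difference is only a possibility.
- **That the serious-event rate would rise by a stated amount.** Adding events to the 5% in Section 1.6 would assume that every excluded patient has a serious event. That 5% was reported after chemoembolization procedures, and the commonest events in it are liver abscess and infarction, so it does not describe attempts where nothing was injected. If failures did carry 5%, 0.3 to 3 of them would account for 0.015 to 0.15 events, with no change in the expected rate.

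**Conclusion.** The concern holds as a conflict over who is in the safety summary. Taken literally, the exclusion rule lets events from an attempted procedure, including a complication that prevented injection, drop out of the summary and its 3-4 week follow-up. Other sections point the opposite way, and no defined safety set settles the matter. The result could be an understated toxicity frequency.

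The size is unknown. The range of 0.3 to 3 failures in 30 attempts rests entirely on an assumed failure rate of 1-10%, and how often failures carry an event is not known either. Serious events remain individually reportable. The point should be corrected because the rule can select on the outcome and is cheap to repair, but it affects a descriptive secondary outcome and leaves the PK comparison untouched.

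**What to change.** 1. In the synopsis and Sections 2.2, 5.5 and 7.2, state that technical failure excludes a patient from the PK analysis only.
2. In Section 7.2 or 7.3, define the safety set as every patient in whom the cTACE procedure was started, summarised by assigned arm. With this definition, whether a partial administration counts as a failure no longer affects the safety summary.
3. In Section 6.3, collect adverse events from the attempt through 3-4 weeks, whether or not material was given.
4. Reword Section 8.2 so that a CRF is required for every patient in the safety set, and Section 4.2 so that it says which analyses a consented patient is counted in.

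The cost is wording in a handful of places and adverse-event follow-up for a few extra patients (0.3 to 3 expected under the assumed range). The reported safety rate may be somewhat less favourable. Treatment and PK analysis do not change.

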## 6. Adverse Event Collection and Reporting Requirements

### 6.1 Definitions

An Adverse Event (AE) is defined as any new untoward medical occurrence or worsening of a pre-existing medical condition in a patient and that does not necessarily have a causal relationship with this treatment. An AE can therefore be any unfavorable and unintended sign (including abnormal laboratory finding, for example), symptom, or disease temporally associated with the treatment.

A Serious AE (SAE) is an untoward medical occurrence that at any dose produces any of the following outcomes:

- Results in death;
- Is life threatening (defined as an event in which the subject was at risk of death at the time of the event; it does not refer to an event which hypothetically might have caused death if it were more severe):

- Requires inpatient hospitalization or causes prolongation of existing hospitalization (see NOTE below for exceptions);
- Results in persistent or significant disability/incapacity;
- Is a congenital anomaly/birth defect;
- Is an important medical event (defined as a medical event(s) that may not be immediately life-threatening or result in death or hospitalization but, based upon appropriate medical and scientific judgment, may jeopardize the subject or may require intervention [e.g., medical, surgical] to prevent one of the other serious outcomes listed in the definition above). Examples of such events include, but are not limited to: intensive treatment in an emergency room or at home for allergic bronchospasm; blood dyscrasias or convulsions that do not result in hospitalization.

NOTE:

The following hospitalizations are not considered SAEs:

- Admissions as per protocol for a planned medical/surgical procedure;
- Routine health assessment requiring admission for baseline/trending of health status (e.g., routine colonoscopy);
- Medical/surgical admission for purpose other than remedying ill health state and was planned prior to entry into the study. Appropriate documentation is required in these cases;
- Admission encountered for another life circumstance that carries no bearing on health status and requires no medical/surgical intervention (e.g., lack of housing, economic inadequacy, care-giver respite, family circumstances, administrative).

## 6.2 Adverse Event Coding

CTCAE term (AE description) and grade: the descriptions and grading scales found in the revised NCI Common Terminology Criteria for Adverse Events (CTCAE) version 4.0 will be utilized for all AE reporting.

## 6.3 Adverse Event Capture and Reporting

Risks associated with the research procedures are expected to be minimal, and are involved with the drawing of blood and the placement of the IV catheter (second sheath). They include pain, bruising, swelling and bleeding when the catheter is placed. There is also a risk of infection at the IV site, and very rarely, nerve damage.

HIC #: 1506016008  
[name]

Adverse Events are collected through 3-4 weeks post cTACE and documented for each patient on the AE case report form (CRF). The AEs are transcribed onto a study-specific electronic AE log which is reviewed regularly by the PI and is available for the IRB and monitoring committees for review.

Study deviations (protocol deviations: PDs) are collected and reported in the same way as the AEs are managed. PDs are collected through 3-4 weeks post cTACE, and documented on CRFs and into PD electronic logs, which are reviewed regularly by the PI and available for IRB and monitoring committees for review.

Unanticipated Problems Involving Risks to Subjects and Others (UPIRSOs) that may require a temporary or permanent interruption of study activities will be reported immediately (if possible), followed by a written report within 5 calendar days of the Principal Investigator becoming aware of the event to the IRB (using the appropriate forms from the website) and any appropriate funding and regulatory agencies. The investigator will apprise fellow investigators and study personnel of all UPIRSOs and adverse events that occur during the conduct of this research project via email as they are reviewed by the PI. The Cancer Center Protocol Review Committee (PRC), Yale Cancer Center Data and Safety Monitoring Committee (DSMC), study sponsor, funding and regulatory agencies will be informed of serious adverse events within 5 days of the event becoming known to the Principal Investigator.

## 7. Statistical Methods

### 7.1 Primary Outcome Variable

Pharmacokinetic profile of doxorubicin and doxorubicinol after cTACE for each patient:

- Parameters of PK analysis including peak of the plasma concentration ( $C_{max}$ ), time of maximum concentration, and area under the concentration time-curve (AUC).
- PK profiles for each patient will be correlated with toxicity and tumor burden (size of target lesion), BSA and gender.
- Comparison of PK profile between lobar administration and superselective administration.

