**Statistical methods:**

**Primary outcome variable:**

**Pharmacokinetic profile of doxorubicin and doxorubicinol after cTACE**

Pharmacokinetic parameters to be measured for each patient:

- Peak of the plasma concentration, time of maximum concentration, and area under the concentration-time curve (AUC).
- Pharmacokinetic profiles for each patient will be correlated with toxicity and tumor burden (size of target lesion), BSA, gender.
- PK profiles of lobar cTACE as compared to that of super-selective cTACE.

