## 3. Subject Selection

### 3.1 Subject Selection

Patients must have histologically, cytologically, or radiologically confirmed liver dominant or liver only malignancy. Patients must have an ECOG performance status of 0-1 at study entry and maintain a Child-Pugh class of A-B without significant liver decompensation (see Tables below). There must be measurable or evaluable disease that will be directly treated with intrahepatic therapy (as defined by Response Evaluation Criteria in Solid Tumors [RECIST] 1.1).

GRADE	ECOG PERFORMANCE STATUS
0	Fully active, able to carry on all pre-disease performance without restriction
1	Restricted in physically strenuous activity but ambulatory and able to carry out work of a light or sedentary nature, e.g., light house work, office work
2	Ambulatory and capable of all self-care but unable to carry out any work activities; up and about more than 50% of waking hours
3	Capable of only limited self-care; confined to bed or chair more than 50% of waking hours
4	Completely disabled; cannot carry on any self-care; totally confined to bed or chair
5	Death

**ECOG Performance Status:** describes a patient's functional level in terms of self-care and physical activity.

Parameter	Points Assigned		
	1	2	3
Ascites	Absent	Slight	Moderate
Bilirubin, mg/dL	≤ 2	2-3	> 3
Albumin, G/dL	> 3.5	2.8-3.5	< 2.8
Prothrombin Time			
Seconds over control	1-3	4-6	> 6
INR	< 1.7	1.8-2.3	> 2.3
Encephalopathy	None	Grade 1-2	Grade 3-4

**Child-Pugh Classification of Liver Disease Severity:** Modified Child-Pugh classification of liver disease severity according to the degree of ascites, the plasma concentrations of bilirubin and albumin, the prothrombin time, and the degree of encephalopathy. A total score of 5-6 is considered grade A (well-compensated disease); 7-9 is grade B (significant functional compromise); and 10-15 is grade C (decompensated disease). These grades correlate with one-year and two-year percent survival; grade A – 100 and 85 percent; grade B – 80 and 60 percent; and grade C – 45 and 35 percent, respectively.

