### 3.2 Inclusion Criteria

Inclusion criteria as follows:

1. Patient's age is ≥ 18 years.
2. Histologically, cytologically, or radiologically confirmed liver dominant or liver only malignancy.
3. Preserved liver function (Child-Pugh A-B class) without significant liver decompensation.
4. Eastern Cooperative Oncology Group (ECOG) performance status of 0-1 at study entry.
5. Measurable or evaluable disease that will be directly treated with intrahepatic therapy (as defined by Response Evaluation Criteria in Solid Tumors [RECIST] 1.1).

6. Suitable for TACE, based on blood parameters such as platelet count, bilirubin, and international normalized ratio.
7. May be enrolled with a history of prior liver directed chemoembolization if chemoembolization to the target lesion occurred > 1 year prior to enrollment date. TACE to different targets within 1 year prior to enrollment date, radioembolization to target location, or other form of intra-arterial therapy will not exclude subjects.

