### 3.3 Exclusion Criteria

Exclusion criteria as follows:

1. Serum total bilirubin > 3.0 mg/dL.
2. Creatinine > 2.0 mg/dL
3. Platelets < 50000/ $\mu$ L
4. Complete portal vein thrombosis with reversal of flow.
5. Ascites (trace ascites on imaging is acceptable).

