### 4.3 Screening Assessments

Assessment completed in the initial clinic visits (pre-consent), as part of standard of care assessments, may be used as part of the study screening assessment.

- Detailed medical history including previous cancer history and cancer treatment. Any additional relevant medication taken one year prior to study start will also be recorded.
- History and physical exam (including vital signs, ECOG-PS assessment, height, weight) within 30 days of cTACE.
- Chemistry panel: Aspartate aminotransferase (AST), alanine aminotransferase (ALT), bilirubin (total and direct), alkaline phosphatase (AP), total protein, albumin, calcium, phosphate, glucose, creatinine, blood urea nitrogen (BUN).
- Electrolyte panel: sodium, potassium, chloride.
- Complete blood count: hemoglobin, hematocrit, platelet count, white blood cell count (WBC). WBC should include differential neutrophil, lymphocyte, monocyte, basophil, and eosinophil counts.
- Prothrombin time and INR.
- Appropriate tumor marker: alpha feto-protein (AFP), carcinoembryonic antigen (CEA), CA 19-9, etc.
- Serum or urine pregnancy test for women of childbearing potential (must be negative)
- Contrast enhanced MRI of the liver within 30 days of treatment. A CT may be used if a MRI would be improbable to obtain.

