### 7.3 Statistical Plan

Up to 40 patients may be consented in order to enroll 30 patients, and to account for patients who are unable to complete sample collection for the PK (80% of planned draws). 15 patients will be enrolled into the lobar cTACE arm and 15 patients will be enrolled into the superselective cTACE arm.

We have assumed a clinically significant change in doxorubicin exposure would be 50%. In order to have 80% power to detect a 50% change with a 5%  $\alpha$ , the sample size varies depending on the variability noted with TACE therapy. In the Varella trial utilizing cTACE with a Lipiodol doxorubicin formulation, the variability was reported as 30% Coefficient of Variation (CV). In our recent trial (J1306) utilizing TACE with a Drug Eluting Bead (DEB) doxorubicin formulation, the variability was reported as 90% CV. We anticipate the Lipiodol formulation to behave more like the Varella trial with 15 patients allowing for slightly higher variability.

*%CV	30%	43%	90%
Expected Sample Size	8	15	58

\*Methodology/calculator accessed from the websites below on 11/6/2014:

[https://www.statstodo.com/SSizBioequiv\\_Tab.php](https://www.statstodo.com/SSizBioequiv_Tab.php)

[https://www.statstodo.com/SSizBioequiv\\_Pgm.php#](https://www.statstodo.com/SSizBioequiv_Pgm.php#)

Continuous variables will be reported as means and standard deviations, medians and ranges, or both. Categorical variables will be reported as numbers and percentages. Pharmacokinetic parameters will be calculated by standard noncompartmental methods using Phoenix WinNonlin 6.1 (Pharsight, Mountain View, CA) for each patient. Pharmacokinetic parameters will be summarized using descriptive statistics.

Comparisons of the pharmacokinetic profiles between the lobar cTACE group and the superselective cTACE group will be performed using the Mann-Whitney U test. Correlations between pharmacokinetic profiles and clinical toxicities will be performed using the Kruskal-Wallis one-way ANOVA test. Correlations between the pharmacokinetic profiles and tumor burden will be performed with the Spearman's correlation coefficient. A P value < 0.05 will be considered statistically significant in all cases.

HIC #: 1506016008  
[name]

Interim analysis:

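### Baseline liver function enters no planned PK analysis, so it is an unexamined source of PK variability and a possible confounder of the non-randomised lobar versus superselective comparison

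*Combined protocol and SAP*

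**What the plan says.** The list of PK correlates appears three times, in the synopsis and in sections 2.1 and 7.1 ("PK profiles for each patient will be correlated with toxicity and tumor burden (size of target lesion), BSA and gender"). Section 7.3 then names three procedures: Mann-Whitney for the arms, Kruskal-Wallis for toxicity, and a rank correlation for lesion size ("Correlations between the pharmacokinetic profiles and tumor burden will be performed with" Spearman's coefficient). A P value below 0.05 counts as significant throughout.

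On eligibility, section 3.2 requires "Preserved liver function (Child-Pugh A-B class) without significant liver decompensation", and the bilirubin exclusion in section 3.3 is "Serum total bilirubin > 3.0 mg/dL". Section 3.1 describes class A as well compensated and states that "7-9 is grade B (significant functional compromise").

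The screening panel in section 4.3 includes "bilirubin (total and direct), alkaline phosphatase (AP), total protein, albumin", and prothrombin time with INR is listed separately.

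Section 5.1 leaves the choice of arm to the principal investigator or a designated radiologist. Section 1.5 says that a superselective or subsegmental approach could be used in "patients who may be contraindicated for conventional nonselective TACE due to severe cirrhosis and risk of serious ischemic complications".

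**The concern.** The trial measures plasma doxorubicin and a metabolite after injection into the liver. Baseline liver function is an obvious candidate to explain differences between patients, at least as much as gender, which is listed. About half the patients are to have primary liver cancer and half secondary, and section 1.2 ties the prognosis of HCC to underlying cirrhosis, so background liver function may vary considerably.

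Two things are at stake. First, unexplained spread reduces the precision of the PK summaries and the power of the arm comparison. Second, the arms are not randomised, so any difference in liver function between them would be read as an effect of technique. If class B patients had higher exposure and were more common in the superselective arm, they would mask the lower serum concentration that section 1.5 conjectures. As written, the analysis would not show whether either has happened.

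**Working it through.** **1. The plan's own figures.** Section 7.3 gives 8, 15 and 58 patients at CV 30%, 43% and 90% (80% power, 50% change, 5% alpha). A parallel-group equivalence-type formula on the raw scale, n = 2(CV/0.5)² × (t₀.₉₅ + t₀.₉₀)² with 2n − 2 degrees of freedom, gives 8, 14 and 57 per arm. At CV 43%: 2 × 0.86² = 1.479; (1.706 + 1.315)² = 9.12; the product is 13.5, so 14. The figures reproduce to within one patient and are not in dispute.

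**2. Is the A-B range really open?** By the table in section 3.1: no ascites (1) + bilirubin 2-3 (2) + albumin below 2.8 (3) + INR 1.8-2.3 (2) + no encephalopathy (1) = 9. That is class B and breaches none of the numeric limits in section 3.3. Scores from 5 to 9 remain possible, although the general conditions on decompensation and on suitability for TACE may exclude some of these patients.

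**3. Effect on spread.** Assumptions: log-normal AUC; class B lowers clearance by 20%, 40% or 50%, so AUC rises by k = 1.25, 1.67 or 2.0; one third of patients are class B. Pooled CV = √(exp(σ² + (ln k)² × 2/9) − 1), with σ² = ln(1 + CV²) within class.

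- Within-class CV 43% (σ = 0.412): pooled CV 44.5%, 50.6%, 56.4%.
- Within-class CV 30%: pooled CV about 32%, 39%, 46%.

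The documents do not say whether the reported 30% already mixes classes. If it does not, the 43% allowance is exceeded only near a halving of clearance.

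**4. Effect on the arm comparison.** 15 per arm, within-class CV 43%, each patient's class drawn at random with the arm's probability, two-sided Mann-Whitney at 5%, at least 4,000 simulated trials per setting. With no technique effect, the geometric mean AUC ratio (superselective to lobar) is k^(difference in class B share).

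| Class B, lobar vs superselective | AUC ratio, k = 1.25 to 2.0 | Rejection with no technique effect |
|---|---|---|
| 30% vs 40% | 1.02-1.07 | about 5-6% |
| 20% vs 40% | 1.05-1.15 | about 5-10% |
| 20% vs 60% | 1.09-1.32 | about 8-29% |

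Now suppose that lobar exposure is truly 1.5 times superselective exposure. Mann-Whitney power is about 69% with no class B effect. For clearance reductions of 20%, 40% and 50% it falls to about 57%, 36% and 25% at 20% vs 40%, and to about 47%, 17% and 8% at 20% vs 60%.

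**5. Does adjustment help?** In the 20% vs 60% setting, a linear model of log AUC on arm and class keeps the error rate at about 5% and power at about 63-65%. Restricting the same setting to class A leaves 12 vs 6 patients. Power for a 1.5-fold difference is then about 39%, against about 70% with 15 vs 15 and no class B effect.

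**6. What 30 patients can show.** Smallest Spearman correlation detectable with 80% power at two-sided 5%: tanh((1.960 + 0.842) × √(1.06/27)) = tanh(0.555) = 0.50.

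**The case against.** The strongest case against is that the mechanism and every figure for its size come from outside the documents. No section says how doxorubicin is cleared, whether Child-Pugh class changes AUC or the metabolite ratio, or how many class B patients are expected. That stands: the figures in steps 3 to 5 are illustrations. They model AUC only, and the large distortions need a threefold imbalance.

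A reader might infer from section 1.5 that poor liver function will steer patients into the superselective arm. The documents do not support this. That sentence concerns severe cirrhosis, which the requirement of preserved function, the bilirubin limit and the ascites exclusion largely screen out. Section 5.1 bases assignment on imaging and history, and section 1.5 links the lobar technique to multiple lesions within a lobe. The sentence shows a possible route, not an expected one.

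A reader might also infer that the trial deliberately mixes very different livers. No reason for admitting both classes is given, and the exclusions narrow the range, though they do not close it.

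Further objections are that the synopsis says the study is not hypothesis driven, that section 7.3 promises general descriptive reporting, and that section 6.1 counts abnormal laboratory findings as adverse events, so liver tests may reach the toxicity correlation. These answer little. Section 7.3 sizes the study for a 50% change in exposure and tests the arms at 5%. The descriptive text names neither liver function nor a breakdown by arm. Adverse events after treatment are not baseline function. It is true that the data are kept and could be explored later, but without the protection of having been specified in advance.

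Finally, a careless fix would do harm. AUC and Cmax for two analytes plus one ratio, each against bilirubin and albumin, make 5 × 2 = 10 tests. If independent and null, they give 1 − 0.95¹⁰ = 40% chance of at least one P < 0.05. That stands and shapes the fix.

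**Conclusion.** The omission is certain: no planned PK analysis uses Child-Pugh class, bilirubin, albumin or INR, although eligibility leaves scores of 5 to 9 open and the arms are not randomised. The consequence is a gap in what the analysis can show, not a demonstrated bias. The distortion is negligible under mild imbalance and serious only if class B has a large effect on clearance and the arms differ sharply in class B share. Both conditions are assumptions here, as is the within-class CV of 43%. The point is worth acting on because the lobar versus superselective result cannot be interpreted with confidence without knowing whether liver function was balanced.

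**What to change.** Amend sections 2.1, 7.1 and 7.3 and the synopsis as follows.

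1. Tabulate baseline Child-Pugh class or score, bilirubin and albumin by arm.
2. Keep the Mann-Whitney comparison and add a sensitivity analysis of log AUC and log Cmax between arms, adjusted for or stratified by baseline Child-Pugh class or score. Use all patients, not class A only.
3. Report Spearman correlations of the PK parameters with baseline bilirubin and albumin as exploratory estimates with confidence intervals, and exempt them explicitly from the general 0.05 significance rule.

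The laboratory values are already collected at screening and Child-Pugh class is already needed for eligibility, so no patients, visits or samples are added. The cost is a few lines of text and slightly more exploratory analysis. A wide interval around a correlation should not be read as showing that liver function has no effect.
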